In Study OSCO-P1202, multiple oral doses of SKI-O-703 200 mg once daily (QD), 400 mg QD, and 200 mg twice daily (BID) were safe and well tolerated by the healthy male and female subjects. There were no deaths or SAEs; however, 1 subject reported TEAE of back pain that led to discontinuation of 200 mg SKI-O-703 BID. Overall, 7 subjects (29.2%) reported a total of 17 TEAEs; of these, 2 subjects (33.3%) reported 6 TEAEs after receiving placebo and 5 subjects (27.8%) reported 11 TEAEs after receiving SKI-O-703. The most commonly reported TEAEs were nausea and headache, each were reported by 2 subjects (33.3%) in the 200 mg SKI-O-703 BID treatment group and by 1 subject (16.7%) in the placebo group. All TEAEs were considered mild or moderate in intensity, and both moderate TEAEs occurred in the placebo group. Except for 1 subject who reported ongoing TEAEs of pyuria and chlamydial infection, all TEAEs resolved by the end of the study. No apparent treatment- or dose-related trends were observed in clinical laboratory values, physical examination findings, or 12-lead electrocardiogram (ECG) results. There was a slight trend in the mean increase of systolic blood pressure from baseline in the 200 mg BID group at Days 16 and 21, and diastolic blood pressure values at Days 16 and 21 also demonstrated a slight trend of a mean increase for all doses of SKI-O-703. There were no significant changes in systolic and diastolic blood pressure for all doses of SKI-O-703 versus placebo at Days 16 and 21.

Pharmacokinetics

[figure not shown]
Pharmacodynamics

[figure not shown]

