3.1.1 Dose Interruption and Reduction

Adverse Events:

It is recognized that some AEs may require dose adjustment or study drug discontinuation. Guidelines for dose reduction are outlined in Table 3-1.

Table 3-1 Guidelines for Dose Interruption and Reduction^a

AE	Occurrence ^b	Action
ALT or AST elevations (range 3 to 5 \times ULN) or ALP $>3 \times$ ULN and $>2 \times$ baseline	First	
 • If asymptomatic (no nausea, anorexia, vomiting), repeat test within 72 hours^c and, if stable or lower, may continue dosing of study drug. • If on repeat test value has increased further but remains $<5 \times$ ULN and asymptomatic, withhold study drug and retest weekly until values becomes stable. When stabilized to $<5 \times$ ULN, continue dosing with the study drug. • If symptomatic or $>5 \times$ ULN, withhold csDMARDs and study drug. Follow the subject weekly until symptoms abate and values return to baseline per confirmation from central laboratory, at which time csDMARDs may be restarted at the prior dose and study drug may be restarted at a reduced dose by skipping one of the doses. 
Note: Discontinue study drug permanently if the ALT elevation is accompanied by an elevation in direct bilirubin to >2 mg/dL (34.2 mmol/L).

	Second	Discontinue study drug permanently.
ANC $<1500/\text{mm}^3$ or $<1.50 \times 10^9/\text{L}$	First	Study drug must be withheld. Repeat the test weekly until value return to baseline or $\geq 1500/\text{mm}^3$ or $\geq 1.5 \times 10^9/\text{L}$, and then restart at a reduced dose by skipping one of the doses.
	Second	Discontinue study drug permanently if the intolerance reoccurs or persists.
Sustained increased systolic (>170 mm Hg) or sustained increased diastolic (>100 mm Hg) blood pressure in a previously normotensive subject	First	
Study drug may be withheld and then restarted at a reduced dose by skipping one of the doses.
 
Irrespective of study drug dose adjustment, subjects who develop a sustained increased systolic (>140 mm Hg) or a sustained increased diastolic (>90 mm Hg) blood pressure should be started on antihypertensive medications (ie, diuretics, calcium channel blockers, ACE inhibitors, etc.) or have their antihypertensive regimen adjusted if already on any antihypertensive agent.

	Second	Discontinue study drug permanently if the hypertension reoccurs or persists.

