7.1. Prior and Concomitant Medications

Medications reported on the Prior and Concomitant Medications CRF will be coded using the World Health Organization Drug Dictionary (WHODD) Enhanced B3 March 2018 version and grouped into relevant categories based on the Anatomical Therapeutic Chemical (ATC) coding scheme.

A prior medication will be any medication stopped prior to the first dose of study drug.

A concomitant medication will be any medication that is either initiated before the first dose of study drug, or initiated on/after the date of the first dose of study drug, and continued during the study treatment period.

Frequency table will be provided by treatment group and overall for prior medications based on the Safety set. The number and percentage of subjects who have prior will be presented by treatment group and overall for each therapeutic drug class (ATC level 2) and generic drug names, with therapeutic drug class and generic drug name within each therapeutic drug class in a decreasing order of overall frequency (then the frequency within treatment groups from high dose to low dose and placebo, if applicable). Similar frequency tables will be provided by treatment group for permitted and prohibited concomitant medications based on the Safety set.

The list of prohibited concomitant medications should be reviewed and finalized by sponsor designee prior to the final database lock.

A listing of prior and concomitant medications by subject will be provided, with an indicator to identify the prior and concomitant medications.

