9.4. Vital Sign Measurements

Vital sign measures will include sitting systolic and diastolic blood pressures (mmHg), pulse rate (beats/ minute), respiratory rate (breaths/ minute) and oral temperature (°C).

Summary statistics of baseline, observed value and change from baseline will be provided by treatment group over time. Frequency summaries of shift from baseline to post-baseline visits by normal indicator (in terms of low, normal and high) will be provided for pulse rate, respiratory rate and blood pressure. The normal ranges are defined as: 60 to 100 beats/minute for pulse rate, 12 to 20 breaths/minute for respiratory rate, 36.5 to 37.5 °C for oral temperature, 90 to 140 mmHg for systolic blood pressure, and 60 to 90 mmHg for diastolic blood pressure. The low

abnormality is defined as any value lower than the low limit of normal range, and the high abnormality is defined as any value higher than the high limit of normal range.

A subject data listing of all vital signs data will be presented by subject identifier, date of collection and vital sign parameter, with abnormality indicated.

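### SAP 9.4 does not account for antihypertensives started at Table 3-1's 140/90 limit, so later-visit blood pressure summaries would be attenuated if the drug raises blood pressure

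*Protocol*

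**What the plan says.** **Treatment guideline.** The blood pressure row of Table 3-1 (protocol 3.1.1) is headed "Sustained increased systolic (>170 mm Hg) or sustained increased diastolic (>100 mm Hg) blood pressure in a previously normotensive subject". Inside that row, and whether or not study drug is adjusted, it adds that subjects with systolic sustained above 140 or diastolic sustained above 90 "should be started on antihypertensive medications (ie, diuretics, calcium channel blockers, ACE inhibitors, etc.) or have their antihypertensive regimen adjusted". The word *sustained* is not defined.

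**Planned blood pressure analysis.** SAP 9.4 says "Summary statistics of baseline, observed value and change from baseline will be provided by treatment group over time". It also plans shift tables from baseline to post-baseline visits, using low, normal and high. The normal ranges are "90 to 140 mmHg for systolic blood pressure, and 60 to 90 mmHg for diastolic blood pressure", and "the high abnormality is defined as any value higher than the high limit of normal range". SAP 9.4 gives no rule for readings taken after an antihypertensive has been started or increased.

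**Where the treatment is counted.** SAP 7.1 tabulates concomitant drugs by therapeutic class, generic name and arm. It defines concomitant as "any medication that is either initiated before the first dose of study drug, or initiated on/after the date of the first dose", provided use continues into the treatment period. SAP 9.1 tabulates treatment-emergent adverse events (TEAEs) by preferred term and arm. Hypertension is not among the events of special interest in SAP 9.2.

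**The concern.** The level at which sites are told to treat is also the level at which the SAP starts to call a reading high. A subject whose pressure is pushed past 140/90 is, if the guideline is followed, treated before later visits. Those later readings reflect the study drug and the antihypertensive together, and SAP 9.4 summarises them as if only the study drug had acted. If the drug raises blood pressure, this happens more often on active arms than on placebo.

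Blood pressure is a sensible place to look carefully. Cardiovascular effects are a named potential risk (protocol 1.5). For the multiple-dose study, protocol 1.1 reports: "There was a slight trend in the mean increase of systolic blood pressure from baseline in the 200 mg BID group". The 400 mg BID regimen has not been given to humans before (protocol 1.3). Vital signs compared with placebo are part of a secondary endpoint (protocol 7.2). At stake is how well the planned tables would show a real effect at Weeks 4, 8 and 12.

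**Working it through.** **1. Compare the limits.** Table 3-1: above 140 systolic or above 90 diastolic. SAP 9.4: high is above 140 or above 90. They are identical.

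**2. Look for a table that isolates the treatment.**
- SAP 7.1 pools drugs begun before first dose with drugs begun after it, and does not tabulate dose increases. Only uncontrolled hypertension is excluded at entry, so established antihypertensive users can enrol and would sit in the same rows as new users.
- Protocol 6.4.2 sends clinically significant vital sign changes to the adverse event page. Protocol 6.4.5.2 reserves the term hypertension for systolic above 160, diastolic above 100, or a clinically significant rise that requires a change to the antihypertensive regimen. A first drug started at 141 to 160 systolic should therefore be recorded as an event, but not clearly under that term.
- SAP 9.3 gives graded laboratory tests a shift to the worst post-baseline grade. SAP 9.4 has no counterpart for blood pressure.

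**3. Direction of the effect.** Let *d* be the true drug effect, *h* the fall produced by an antihypertensive, and *pA* and *pP* the proportions treated before Week 12 on active and placebo. Then

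observed Week 12 difference = *d* − *h* × (*pA* − *pP*).

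If *d* = 0, then *pA* = *pP* and there is no bias. If *d* > 0, then *pA* > *pP* and the difference shrinks.

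**4. Illustrative size.** The documents give no blood pressure mean or SD, drug effect, antihypertensive effect or definition of *sustained*. Every input here is an assumption.

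*Set 1.* Baseline systolic mean 128, between-subject SD 12, visit SD 8, *d* = 6 mm Hg, visits at Weeks 2, 4, 8 and 12, full compliance with the guideline. *Sustained* means one visit above 140 (treated: 52% active, 35% placebo) or two consecutive visits (30% and 18%). For *h* = 10 the formula gives 6 − 10 × 0.17 = 4.3 and 6 − 10 × 0.12 = 4.8. Simulation gives:

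| Rule | *h* (mm Hg) | Week 12 difference | Reduction from 6.0 | Excess above 140 (13.7 points if untreated) |
|---|---|---|---|---|
| One visit | 6 | 4.95 | 17.5% | 10.0 |
| One visit | 10 | 4.28 | 28.7% | 7.3 |
| One visit | 14 | 3.59 | 40.2% | 5.2 |
| Two visits | 6 | 5.25 | 12.5% | 11.4 |
| Two visits | 10 | 4.82 | 19.7% | 9.6 |
| Two visits | 14 | 4.34 | 27.7% | 7.8 |

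*Set 2.* Baseline mean 122, 128 or 134, between-subject SD 12, visit SD 9, baseline below 160, *d* = 0, 3, 5 or 8, *h* = 8 or 12, same two rules.
- With *d* = 0 the observed difference stays within 0.05 mm Hg of zero.
- With *d* from 3 to 8 the mean difference falls by about 9% to 35%.
- The excess of subjects moving from not high at baseline to high at Week 12 falls by about 18% to 64%. For example, at mean 128 and *d* = 5, 9.5 points becomes 3.5 to 7.1.
- In that example the excess ever high at any visit is 16 points with or without antihypertensives, because the first high reading comes before treatment. A worst-post-baseline table would therefore keep the contrast that the Week 12 shift loses.

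**The case against.** **The treatment is not invisible.** A reader might infer that the SAP ignores it altogether. The documents do not support that. Protocol 6.4.2 treats a vital sign change as clinically significant if it may alter medical care, including by therapeutic measures, so starting an antihypertensive for raised pressure should produce an adverse event entry and a row in the TEAE tables. SAP 7.1 counts the drugs by arm. Established users should be roughly balanced by randomization, so excess new use would show, though diluted. This stands. What remains is that neither source isolates new or increased use, and neither changes how the readings themselves are summarised.

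**The triggering reading is not lost.** Shifts are by visit, so the high value appears at its own visit. Week 2 precedes any treatment triggered at a scheduled post-baseline visit, and under a two-visit rule so does Week 4. This also stands; the attenuation is confined to later visits.

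**A pressor effect is not established.** The section of protocol 1.1 that reports the slight trend also reports no significant change versus placebo at Days 16 and 21. Any understatement is conditional.

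**The guideline may bite less than simulated.** The 140/90 sentence sits in a row headed above 170/100 for previously normotensive subjects, in a table of guidelines that its footnote calls examples. One reading above 140 is a generous meaning of *sustained*. The 40% figure depends on that meaning; the two-visit rule gives 12.5% to 27.7%.

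**The loss is small against noise.** With visit SD 8, the SD of change is 8 × √2 = 11.3, and with 37 per arm the standard error of a difference is 11.3 × √(2/37) = 2.6 mm Hg. The Set 1 losses, 6 − 5.25 = 0.75 to 6 − 3.59 = 2.41 mm Hg, are below one standard error. An excess of 13.7 points is about 5 subjects in an arm of 37. The tables are descriptive, with no test. This limits the weight of the point, although the attenuation is systematic and runs one way whenever the drug effect is real.

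**Conclusion.** The point holds in conditional form. The limits match exactly, SAP 9.4 makes no allowance for the treatment that Table 3-1 calls for, and no planned table isolates antihypertensives started or increased after first dose. If the drug raises blood pressure and sites follow the guideline, later-visit mean changes and shifts would be attenuated towards no difference. The documents cannot fix the size; about 10% to 40% of the Week 12 mean difference is an illustration that rests on the assumed inputs and full compliance.

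Two stronger readings go beyond the documents: that the planned summaries do understate a pressor effect, which presumes an effect not shown, and that the shift tables hide high readings, when only those after treatment are affected. The lack of a worst-post-baseline blood pressure shift is the sharper gap. This is a worthwhile, low-cost improvement to the safety analysis; it does not touch the primary efficacy result.

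**What to change.** Amend SAP 9.4 before unblinding:

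- **(a)** Flag, blinded, every antihypertensive started or increased after first dose, and tabulate the number and percentage of such subjects by arm. Protocol 5.8 already collects dates, doses, changes and reason for use.
- **(b)** Add a worst-post-baseline blood pressure shift, and a by-visit composite: reading high, or antihypertensive started or increased since first dose.
- **(c)** As a supportive summary only, repeat the change from baseline without readings taken after such a start or increase. This selectively removes high-pressure subjects, more of them on active arms if the drug raises pressure, so it can itself lean towards no difference and must be read beside (a) and (b).

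Keep the planned as-observed summary. The cost is SAP wording, the blinded medication flag and a few extra tables; no new data are needed.

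Separately, the scope of the 140/90 sentence should be reconciled with the heading of the Table 3-1 row that contains it: the heading is limited to previously normotensive subjects above 170/100, while the sentence uses lower limits and also covers subjects already on antihypertensives. Which clinical rule applies is for the sponsor to settle.

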3.1.2 Rationale of Study Design

This double-blind, placebo-controlled study is designed to evaluate the efficacy, safety, tolerability, PK, and PD of SKI-O-703 in subjects with RA who have had an inadequate response to csDMARDs or previous 1, 2 or more TNF α inhibitors. The results of this study will guide on further clinical evaluation of SKI-O-703 in adult subjects with moderately to severely active RA. The double-blind, placebo-controlled design has been selected to minimize bias in the evaluation of the safety, efficacy, PK, and PD.

Serial blood samples (5 mL) for PK assessment of SKI-O-592 and its metabolites (M2 and M4) from a subset of 6 subjects per cohort will be obtained from this study, which is common approach in Phase 2 studies for PK sampling. Full PK profile from subset of subjects in this study would help to define the underlying structure of the PK model, which in turn would help refine the sparse sampling approaches needed for later Phase 3 studies leading to a better population PK analysis in Phase 3.

The 2 most widely used sets of improvement criteria in clinical trials are the ACR improvement criteria using all 7 core set variables, and the EULAR response criteria based on the disease activity score (DAS), an index using only 3 or 4 core set variables. Studies in RA have interchangeably used these outcome measures as primary endpoints in clinical trials. Including more variables in a combined index such as the ACR does not increase the validity of these outcome measures (van Gestel et al 1999). The performance of the EULAR criteria and the ACR improvement criteria has been compared in different clinical trials (Prevoo et al 1995). It was shown that they behave similarly with less than 5% discrepancy in responder status.

The power of a statistical test is typically a function of the magnitude of the treatment effect, the designated Type I error rate (α , risk of false-positive result) and the sample size (n). When designing a trial, it is important to decide upon the desired study power (typically 80%) and calculate the necessary sample size to achieve this goal. Since it is often not feasible to conduct large trials during early stage of development, it is necessary to identify the strategies to optimize the statistical power of smaller studies. Continuous variables are

significantly better suited to improving statistical power in small trials than dichotomous variables.

In this study, DAS28- high sensitivity C-reactive protein (hsCRP) is selected as the primary endpoint since it is a continuous variable whereas ACR20 is a dichotomous variable. Statistical implications of using a dichotomous variable requires more subjects of any study to show a difference, but for smaller studies such as a Phase 2 study, it would be better powered using a continuous endpoint minimizing the sample size to achieve a primary endpoint of DAS28-hsCRP.

4 Subject Selection and Withdrawal Criteria

4.1 Selection of Study Population

Approximately 148 subjects will be enrolled at multiple sites in the United States, Europe, and South Korea. Subjects will be assigned to study treatment only if they meet all of the inclusion criteria and none of the exclusion criteria.

Deviations from the inclusion and exclusion criteria are not allowed because they can potentially jeopardize the scientific integrity of the study, regulatory acceptability, or subject safety. Therefore, adherence to the criteria as specified in the protocol is essential.

If a subject fails one or more inclusion or exclusion criteria, one re-screening attempt is allowed per subject.

4.1.1 Inclusion Criteria

Each subject must meet all the following criteria to be enrolled in this study:

1. Subject is an adult male or female aged ≥ 18 years old at time of signing the informed consent (or per local customs for ≥ 19 years of age for Korean subjects).
2. Subject has Body Mass Index (BMI) of ≥ 18 and $< 40 \text{ kg/m}^2$ at screening.
3. Subject who has a diagnosis of RA according to the 1987 ACR criteria (Appendix 13.2) or the 2010 ACR/EULAR classification criteria (Appendix 13.3) for at least 6 months prior to Day 1.
4. Subject has active disease at screening and baseline following treatment of RA with inadequate response to csDMARDs or anti-TNF α biological agent(s) as per 2012 update of the 2008 ACR RA treatment recommendations (Singh JA 2012).
 - a. Active disease is defined as:
 - presence of ≥ 5 swollen joints (of 28 assessed) and presence of ≥ 5 tender joints (of 28 assessed), and
 - serum hsCRP concentration $\geq 0.6 \text{ mg/dL}$ (or $\geq 6.0 \text{ mg/L}$; $1 \text{ mg/L} = 9.524 \text{ nmol/L}$) at screening (based on the upper limit of normal [ULN] of laboratory normal

range). Repeat may be allowed once during screening period (after an approval from medical monitor), if the result is considered unexplained/unexpected (eg, not corresponding with clinical disease activity or discordant with recent local result).

b. At least ONE of the following treatments for RA must have been received:

- anti-TNF α biological agent(s): Includes at least 1 of the following treatments, with completed washout period indicated prior to Day 1 dosing

adalimumab (Humira $^{\circledR}$)	60 days washout
etanercept (Enbrel $^{\circledR}$)	30 days washout
infliximab (Remicade $^{\circledR}$)	60 days washout
certolizumab pegol (Cinzia $^{\circledR}$)	60 days washout
golimumab (Simponi $^{\circledR}$)	60 days washout

- csDMARD therapy: Includes at least 1 of the following dosing regimen for at least 90 days of continuous use (prior to Day 1 dosing)*

- MTX 15 to 25 mg/week. If the current MTX dose is <15 mg/week, the subject's intolerance to \geq 7.5 mg dose must be documented in the subject's medical history
 - \leq 3000 mg/day (3 g/day) sulfasalazine
 - \leq 400 mg/day hydroxychloroquine
 - \leq 200 mg/day minocycline
 - \leq 20 mg/day leflunomide

*Note: Combinations of up to 2 csDMARDs are allowed. However, combination of MTX and leflunomide is not allowed. Subjects are allowed to continue taking csDMARD therapy at stable doses (initiated \geq 4 weeks prior to the first dose of study drug) throughout the study period.

a) If subjects have to discontinue csDMARD therapy (except for leflunomide), the washout windows 30 days prior to Day 1 dosing must be observed.

b) If subjects have to discontinue leflunomide due to combination use with MTX before enrollment, the following washout windows must be observed: subjects who discontinued leflunomide and have had successful chelation with 8 g of cholestyramine (3 times daily) for 3 days must wait for 4 weeks prior Day 1 dosing. Subjects who discontinued leflunomide and did not have cholestyramine washout must wait 12 weeks after last dose of leflunomide prior to Day 1 dosing.

5. Subjects taking MTX while on study must be willing to take dietary supplement of oral folic acid (or equivalent, such as folinic acid) at a stable dose.
6. Subject who has adequate renal and hepatic function at screening as defined by the following clinical chemistry results:
 - a. Serum creatinine $<1.5 \times \text{ULN}$ or an estimated creatinine clearance level $\leq 50 \text{ mL/min}$ (by MDRD GFR equation)
 - b. Serum alanine aminotransferase (ALT) $<2.5 \times \text{ULN}$
 - c. Serum aspartate aminotransferase (AST) $<2.5 \times \text{ULN}$
 - d. Serum total bilirubin $<2 \times \text{ULN}$.

Repeat of clinical chemistry laboratory tests may be allowed once during screening period (after an approval from medical monitor), if the initial result is unexpected/unexplained (not due to a known underlying condition or concomitant medications or other known cause).

7. Subject who has the following hematology laboratory test results at screening:
 - a. Hemoglobin $\geq 8.5 \text{ g/dL}$ (International System of Units [SI]: $\geq 85 \text{ g/L}$ or 5.28 mmol/L)
 - b. White blood cell count $\geq 3.5 \times 10^3 \text{ cells}/\mu\text{L}$ (SI units: $\geq 3.5 \times 10^9 \text{ cells/L}$)
 - c. Neutrophil count $\geq 1.5 \times 10^3 \text{ cells}/\mu\text{L}$ (SI units: $\geq 1.5 \times 10^9 \text{ cells/L}$)
 - d. Platelet count $\geq 100 \times 10^3 \text{ cells}/\mu\text{L}$ (SI units: $\geq 100 \times 10^9 \text{ cells/L}$).

Repeat of hematology laboratory tests may be allowed once during screening period (after an approval from medical monitor), if the initial result is unexpected/unexplained (not due to a known underlying condition or concomitant medications or other known cause).

8. Subject who can comprehend the full nature and purpose of the study, including possible risks and side effects, to cooperate with the investigator, to understand verbal and/or written instructions, and to comply with the requirements of the entire study.
9. Subject is informed of the full nature and purpose of the study, including possible risks and side effects, and given ample time and opportunity to read or understand this information, signed and dated the written informed consent before inclusion in the study.
10. A) For both male and female subjects (except subjects in Czech Republic and Republic of Korea), the subject and their partners of childbearing potential must agree to use one of the following medically acceptable methods of contraception during the study and for 6 months following discontinuation of study drug:
 - a. Barrier contraceptives (male condom, female condom, or diaphragm with a spermicidal gel).
 - b. Hormonal contraceptives (implants, injectables, combination oral contraceptives, transdermal patches, or contraceptive rings).
 - c. Intrauterine device.

For subjects and partners considered not of childbearing potential, the following conditions apply:

- a. Menopausal females must have experienced their last period more than 12 months prior to the date of informed consent to be classified as not of childbearing potential.
- b. Male and female subjects and their partners who have been surgically sterilized for less than 6 months prior to the date of informed consent must agree to use any medically acceptable methods of contraception.

B) For subjects in Czech Republic and Republic of Korea, both male and female subjects must agree to take the following steps to reduce the potential for the transmission of genetic material containing the investigational product:

- a. Both male and female subjects, the subject and their partners of childbearing potential must agree to use 2 of the following medically acceptable methods of contraception from the time of randomization, during the study, and for 6 months following discontinuation of study drug, of which:

- One must be a highly reliable method of contraception, such as:
 - o An intrauterine device or intrauterine system implanted for at least 30 days prior to Day 1.
 - o Surgical sterilization of one of the partners for at least 6 months prior to the date of informed consent (assuming this will be the only partner for the whole duration of the clinical trial).
 - o Consistent and correct use of hormonal contraceptives (hormonal implants, injectables, contraception pills, transdermal patches, or contraceptive rings) for at least 30 days prior to Day 1.
- One supplementary barrier method, such as:
 - o Male or female condom always with spermicide (a spermicidal foam/gel/film/cream).
 - o Diaphragm or cervical/vault caps always with spermicide (a spermicidal foam/gel/film/cream).
 - o Double-barrier methods (which means a barrier method used by both partners at the same time), even when used with spermicide, are not considered to be highly reliable contraception methods, and as such, may not be the only forms of contraception used.

One of the other listed highly reliable methods must be used in conjunction with a barrier method.

- b. Female subjects must agree not to breastfeed starting from the time of screening, throughout the study, and until after 6 months following the last dose of study drug.
- c. Male subjects must agree not to donate sperm starting from the time of randomization, throughout the study, and until after 6 months following the last dose of study drug.

For subjects and partners considered not of childbearing potential, the following conditions apply:

- a. Menopausal females must have experienced their last period more than 12 months prior to the date of informed consent to be classified as not of childbearing potential.
- b. Male and female subjects are in a situation of abstinence from heterosexual intercourse from screening until after 6 months following the last dose of study drug when this is in line with the preferred lifestyle of the subject (eg, homosexual women and men or a member of a religious order such as nuns and priests).

